#### **6.2.4 Management of sARRs and Local Injection Site Reactions of Daratumumab SC**

##### **6.2.4.1 Systemic Administration-Related Reactions**

Systemic administration-related reactions are systemic reactions related to daratumumab administration. Subjects should be observed carefully during daratumumab administrations. Trained study staff at the clinic should be prepared to intervene in case of any sARRs, and resources necessary for resuscitation (eg, agents such as epinephrine and aerosolized bronchodilator, medical equipment such as oxygen tanks, tracheostomy equipment, and a defibrillator) must be available at the bedside. Attention to staffing should be considered when multiple subjects will be dosed at the same time.

If an sARR develops during daratumumab SC administration, then the administration should be temporarily interrupted. Subjects who experience AEs during daratumumab administration must be treated for their symptoms. Subjects should be treated with paracetamol (acetaminophen), antihistamine, or corticosteroids, as needed. IV saline may be indicated. For bronchospasm, urticaria, or dyspnea, subjects may require antihistamines, oxygen, corticosteroids, or bronchodilators. For hypotension, subjects may require vasopressors. In the event of a life-threatening sARR (which may include pulmonary or cardiac events) or an anaphylactic reaction, daratumumab should be permanently discontinued.

##### **6.2.4.2 Systemic Administration-Related Reactions of Grade 1 or Grade 2**

If the investigator assesses a Grade 1-2 sARR to be related to administration of trial drug, then the daratumumab administration should be interrupted. When the subject's condition is stable, daratumumab administration may be restarted at the investigator's discretion ([DARZALEX FASPRO USPI, 2021](#)). Refer to the IMP Manual for further details regarding continuation of daratumumab administration.

If the subject experiences a Grade 2 or higher event of laryngeal edema, or a Grade 2 or higher event of bronchospasm that does not respond to systemic therapy and does not resolve within 6 hours from onset, then the subject must be permanently discontinued from daratumumab treatment.

##### **6.2.4.3 Systemic Administration-Related Reactions of Grade 3 or Higher**

For sARR AEs (other than laryngeal edema or bronchospasm) that are Grade 3, the daratumumab administration must be stopped, and the subject must be observed carefully until resolution of the AE or until the intensity of the event decreases to Grade 1, at which point the daratumumab administration may be restarted at the investigator's discretion. Refer to the IMP Manual for further details regarding continuation of daratumumab administration.

If the intensity of the AE returns to Grade 3 after restart of the daratumumab administration, then the subject must be permanently discontinued from daratumumab treatment.

For sARR AEs that are Grade 4, the daratumumab administration must be stopped, and the subject permanently discontinued from daratumumab treatment.

#### **6.2.4.4 Recurrent Systemic Administration-Related Reactions**

If a Grade 3 sARR (or Grade 2 or higher event of laryngeal edema, or a Grade 2 or higher event of bronchospasm) recurs during or within 24 hours after a subsequent daratumumab administration, the subject must be permanently discontinued from daratumumab treatment.

#### **6.2.4.5 Injection Site Reactions**

Skin reactions at or near the injection site (local), including injection site reactions, can happen with daratumumab. Symptoms at the site of injection may include itching, swelling, bruising, pain, rash, bleeding, or redness of the skin. These reactions sometimes happen more than 24 hours after an injection of daratumumab. Monitor for local reactions and consider symptomatic management.

### **6.2.5 Post-Administration Monitoring for Expansion Part A (GEN3014 Single Cohorts) and Expansion Part B (Randomized H2H)**

During treatment Cycle 1, all subjects are required to remain in the clinic after each GEN3014 infusion or daratumumab injection for 4 hours where they will be closely observed. Beyond observation for AEs, vital signs will be measured and blood sampling for laboratory parameters, cytokines, PK and pharmacodynamic measurements will be performed.

If clinically indicated, observation of up to 24 hours post-dose during Cycle 1 is acceptable at the discretion of the investigator.

If a subject has an IRR or sARR of  $\geq$  grade 3 during the infusion or injection, the subject will be required to stay overnight in hospital. If a subject is hospitalized for prolonged monitoring post-infusion or injection, the hospitalization should not be reported as an SAE.

## **6.3 Preparation/Handling/Storage/Accountability**

### **6.3.1 Preparation, Handling, and Storage**

The preparation, handling, and storage of GEN3014 and daratumumab SC are described in the IMP Manual.

#### **6.3.1.1 GEN3014**

GEN3014 must be stored at controlled temperature ranging from 2 to 8 °C (36 to 46 °F).

#### **6.3.1.2 Daratumumab SC**

Daratumumab SC must be stored at controlled temperature ranging from 2 to 8 °C (36 to 46 °F) in the original carton to protect from light ([DARZALEX FASPRO USPI, 2021](#)).

### **6.3.2 Drug Accountability**

The investigator or designee must maintain an accurate record of the shipment and dispensing of trial treatment in a drug accountability log. Drug accountability will be verified by the field monitor during site visits and at the completion of the trial.

For trials using Interactive Response Technology (IRT), the drug accountability must be documented within the system.

When drug accountability has been verified and a copy of the completed drug accountability log has been received by sponsor, the investigator will dispose all used and unused trial treatment and packaging in accordance with the guidance in the trial-specific preparation and administration guideline and local regulations per the trial drug IMP Manual.

## **6.4 Measures to Minimize Bias: Randomization and Blinding**

### **6.4.1 Subject Numbering**

After signing the ICF, subjects will be assigned a unique subject identification number before undergoing any Screening procedure(s).

### **6.4.2 Treatment Assignment**

This is an open-label trial; blinding does not apply. Randomization only applies to Expansion Part B (Randomized H2H).

#### **6.4.2.1 Dose Escalation**

In the Dose Escalation, site personnel must contact the contract research organization (CRO) when a potential subject has been identified. Subjects will be designated by their disease type of either RRMM or R/R AML.

If there is an available enrollment slot in any currently enrolling DL, the site will be given approval to start the screening process. If there is no opening, the subject will be placed on a waiting list, and the site will be alerted of the next available opening either in the currently enrolling DL or at the next opened DL.

#### **6.4.2.2 Expansion Part A (GEN3014 Single Cohorts) and Part B (Randomized H2H)**

In the Expansion Part A (GEN3014 Single Cohorts), subjects will be assigned to 1 of the 4 cohorts: anti-CD38 mAb-naive RRMM, anti-CD38 mAb-refractory RRMM, R/R AML, or R/R DLBCL.

In the Expansion Part B (Randomized H2H), anti-CD38 mAb-naive subjects with RRMM will be randomized in a 1:1 ratio to receive either GEN3014 or daratumumab SC. Subjects will be assigned randomly to 1 of the 2 treatment groups based on a computer-generated randomization schedule prepared before the trial by or under the supervision of the sponsor. The randomization will be balanced by using randomly permuted blocks and will be stratified by body weight at baseline ( $\leq 70$  kg;  $> 70$  kg) CCI [REDACTED]. The IRT will assign a unique treatment code, which will dictate the treatment assignment and matching study drug kit for the subject. The requestor must use their own user identification and personal identification number when contacting the IRT and will then give the relevant subject details to uniquely identify the subject. In order to ensure 40 evaluable subjects in each treatment arm (see Section 4.1.4 and Section 9.2.3), the sponsor may replace subjects by arm rather than stratification factors, if justified.

## **6.5 Compliance**

GEN3014 and daratumumab SC will be administered by qualified site personnel to assure compliance with trial requirements. The date and time of each trial drug administration will be documented.

Intervention start and stop dates/time, including trial drug administration start/stop time for managing IRRs/sARRs, and dates for trial drug delays will also be documented.

## 6.6 Dose Modifications

### 6.6.1 Dose-Limiting Toxicity (Dose Escalation)

The DLT Evaluation Period is defined as the first 28 days of GEN3014 treatment (ie, Cycle 1). Toxicities will be graded for severity according to the National Cancer Institute Common Terminology Criteria for Adverse Events (NCI-CTCAE), v5.0, with the exception of TLS (see Section 10.3.7).

The occurrence of any of the toxicities outlined in this section will be considered a DLT.

- All Grade 5 toxicities
- Hematological toxicities listed below:
  - Grade 4 thrombocytopenia (platelet count  $<25.0 \times 10^9/L$  [ $<25,000/\mu L$ ]) lasting  $>7$  consecutive days not attributable to the underlying disease.
  - Grade 4 neutropenia (neutrophil count  $<0.5 \times 10^9$  cells/L [ $<500/\mu L$ ]) lasting  $>7$  consecutive days not attributable to the underlying disease.
  - Grade 3 and grade 4 febrile neutropenia (neutrophil count  $<1.0 \times 10^9$  cells/L with a single temperature of  $>38.3^\circ C$  [ $100.9^\circ F$ ] or with a sustained temperature of  $\geq 38^\circ C$  [ $\geq 100.4^\circ F$ ] for more than 1 hour) lasting  $>2$  days.
  - Grade 3 and grade 4 hemorrhage associated with thrombocytopenia of  $\geq$  grade 3 requiring platelet transfusion.
  - Grade 4 anemia
- Note: Since bone marrow aplasia is an expected consequence of AML therapies, only persistent pancytopenia lasting  $\geq 14$  days and not related to leukemia infiltration will be considered as a DLT for the R/R AML Cohort. Bone marrow evaluation may be required to determine if marrow aplasia is due to leukemia.
- Non-hematological toxicities:
  - All non-hematological toxicities of grade  $\geq 3$  (severe or life-threatening), **excluding** the following:
    - a. Grade 3 fever ( $>40.0^\circ C$  [ $>104.0^\circ F$ ]) for  $\leq 24$  hours
    - b. Grade 3 hypotension (medical intervention indicated; hospitalization indicated) resolving in  $\leq 24$  hours
    - c. Laboratory values out of normal range that do not have any clinical consequence, are clinically transient in nature and that resolve in  $\leq 3$  days (including electrolyte abnormalities that respond to medical intervention)
    - d. Grade 3 AST and/or grade 3 ALT returning to grade 1 or baseline in  $\leq 7$  days
    - e. Grade 3 nausea that responds to adequate antiemetic treatment in  $\leq 3$  days
    - f. Grade 3 vomiting that responds to adequate antiemetic treatment in  $\leq 3$  days
    - g. Grade 3 diarrhea that responds to adequate antidiarrheal treatment in  $\leq 3$  days

- h. Grade 3 fatigue/asthenia when fatigue/asthenia was present at baseline or that lasts for <14 days
- i. Alopecia (all grades)
- Grade 4 TLS (see Section 10.3.7 for additional information)
- Grade 4 IRR
- Any liver toxicity of elevated ALT or AST  $\geq 3$  times or greater above the upper limit of normal (ULN) with serum total bilirubin of  $\geq 2$  times the upper limit of normal, without findings of cholestasis and in the absence of alternative etiologies

**Note:** AEs of specified grades, regardless of relationship to GEN3014, should be considered relevant for dose escalation decisions, unless the event can clearly be determined to be unrelated to the drug. All of the AEs of specified grades should be classified as DLTs except those that are clearly and incontrovertibly due to the underlying disease or extraneous causes.

The investigator must notify the sponsor immediately of a DLT. Frequent laboratory monitoring of complete blood count (CBC) including differential should be initiated to document start and resolution of hematological AEs. All AEs occurring during the defined DLT evaluation period will be assessed according to the criteria above. All GEN3014-related AEs will be monitored and included in the evaluation of the toxicity profile of GEN3014 unless the event is clearly determined to be unrelated to GEN3014 (eg, disease progression).

#### **6.6.2 GEN3014 Dose Modification Guidance and Stopping Criteria (Dose Escalation and Expansion Part A)**

- No dose modification (increase or decrease) of GEN3014 will be permitted for this trial.
- If a subject experiences a DLT, the subject may continue treatment with GEN3014, if the toxicity recovers to  $\leq$  grade 2 or baseline within 4 weeks from occurrence of the DLT. Continued administration of GEN3014 must be agreed to between the sponsor and the investigator based on a thorough assessment of the event, the duration of the event, and benefit-risk for the subject. In the event a subject experiences a second episode of a DLT with GEN3014, the treatment will be permanently discontinued. Treatment with GEN3014 will be discontinued in the event the DLT is not resolved within 4 weeks.
- If a subject experiences toxicity that would have qualified as a DLT but the event occurs after the DLT evaluation period, the subject's benefit-risk must be thoroughly assessed. Continued treatment with GEN3014 must be agreed between the sponsor and the investigator.
- For the subject who receives treatment beyond the DLT evaluation period, all corresponding AEs that would have met the DLT criteria will be considered for the purpose of determining the RP2D and/or MTD (if reached). For the declaration of the RP2D from the Dose Escalation for further development of GEN3014 in the Expansion, the totality of the data including safety, PK, pharmacodynamics, and preliminary efficacy will be evaluated.
- During the trial, a planned dose of GEN3014 can be postponed for up to 4 weeks due to an AE whether it is considered drug-related or not.

- In case of dose delay of more than 4 weeks from the last trial drug administration due to toxicity, GEN3014 should be discontinued, unless resuming administration of GEN3014 is agreed between the sponsor and the investigator.
- During the trial, the GEN3014 dose can be held for the following laboratory results:
  - a. If platelet count is  $<50 \times 10^9/L$ , hold dose until platelet count is  $\geq 50 \times 10^9/L$ .
  - b. If febrile neutropenia is  $<0.5 \times 10^9/L$ , hold dose until neutrophil count is  $\geq 0.5 \times 10^9/L$ .
  - c. If hemoglobin is  $<8$  g/dL ( $<8$  g/L or  $<5$  mmol/L), hold dose until hemoglobin is  $\geq 8$  g/mL ( $\geq 8$  g/L or  $\geq 5$  mmol/L).

Note: If the investigator deems any of the above cytopenia as bone marrow involvement due to the disease, continuation of GEN3014 treatment can be discussed with the sponsor's medical monitor. Transfusion with blood products and/or administration with granulocyte colony-stimulating factor (G-CSF) is permitted if needed (refer to Section 6.7.3.2).

If a dose delay occurs, then PK and pharmacodynamic assessments should be performed on or relative to the actual day of trial drug administration, not on the original scheduled administration day.

Refer to Section 9.6 for safety stopping criteria for the Expansion cohorts.

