**Table 3-1 Objectives and Endpoints – Dose Escalation**

Objectives	Endpoints
Primary	

 
Determine the RP2D and if reached, the MTD of GEN3014
 
	
 
Incidence of DLTs
 

 
Evaluate the safety and tolerability of GEN3014
 
	
 
Safety: Incidence and severity of AEs and SAEs, including changes in laboratory values, vital signs, ECGs
 
Tolerability: Dose interruptions, delay, and dose intensity
 

Secondary	

 
Characterize the PK properties of GEN3014
 
	
 
Noncompartmental PK parameters (if feasible): 
 
<math>C_{max}</math>
 
<math>t_{max}</math>
 
<math>C_{trough}</math>
 
<math>AUC_{0-last}</math> and <math>AUC_{0-168h}</math>
 
<math>RA_{Cmax}</math> and <math>RA_{AUC}</math>
 
 
 
In addition, a population PK modeling approach may be employed
 

 
Evaluate immunogenicity
 
	
 
Anti-GEN3014 antibodies
 

 
Assess the preliminary anti-tumor activity of GEN3014
 
	
 
ORR
 
CBR
 
DOR
 
TTR
 

 
Assess the clinical efficacy of GEN3014
 
	
 
Progression-free survival (PFS)
 
Overall survival (OS)
 

Exploratory	

 
Assess potential biomarkers predictive of clinical response to GEN3014
 
	
 
CCI
 

 
Assess minimal residual disease (MRD) status
 
	
 
Rate of MRD-negative remission in RRMM
 

 
Explore PK/pharmacodynamic relationship (PK/anti-tumor activity) and PK/safety
 
	
 
Dose concentration response (biomarkers and/or efficacy, safety) relationship
 

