### 5.1 Inclusion Criteria

#### 5.1.1 Inclusion Criteria – Dose Escalation

Each potential subject must fulfill all of the following criteria to be eligible for inclusion in the Dose Escalation part of the trial:

1. Must be at least 18 years of age.
2. Must sign an informed consent form (ICF) prior to any Screening procedures. Where required by local or country specific regulations, each subject must sign a separate ICF if he or she agrees to provide samples for genomic biomarker analysis (deoxyribonucleic acid [DNA] and ribonucleic acid [RNA]).
3. Must have fresh bone marrow samples collected at Screening.
4. Eastern Cooperative Oncology Group (ECOG) performance status (PS) score 0, 1, or 2.
5. Criterion modified per Amendment 2.

5.1 Criterion modified per Amendment 3\_US-1.

5.2 Criterion modified per Amendment 4.

5.3 Has acceptable laboratory test results during the Screening period, as follows:

Parameter		Result
a.	Creatinine clearance (CrCl) or serum creatinine	CrCl $\geq 50$ mL/min estimated by Cockcroft-Gault (see Section 10.5) or serum creatinine $\leq 1.5 \times$ upper limit of normal (ULN)
aUS	CrCl	See Section 10.15.2 for requirements per local health authorities.
b.	Serum alanine aminotransferase (ALT)	$\leq 2.5 \times$ ULN
c.	Serum aspartate aminotransferase (AST)	$\leq 2.5 \times$ ULN
d.	Total bilirubin	$\leq 2 \times$ ULN  Note: A subject with Gilbert's syndrome may be included if total bilirubin is <math>\leq 3 \times</math> ULN and direct bilirubin is <math>\leq 1.5 \times</math> ULN

e.	Hemoglobin	$\geq 8$ g/dL ( $\geq 80$ g/L or $\geq 5$ mmol/L) for RRMM Note: Red blood cell transfusion may be administered during Screening to meet this requirement
f.	Absolute neutrophil count	$>1.0 \times 10^9$ /L ( $>1,000/\mu\text{L}$ ) for RRMM Note: G-CSF may be administered during Screening to meet this requirement
g.	Platelet count	$>50 \times 10^9$ /L ( $>50,000/\mu\text{L}$ ) for RRMM Note: Platelet transfusion may be administered during Screening to meet this requirement
h.	Coagulation Status: Prothrombin time (PT), International normalized ratio (INR), activated partial thromboplastin time (aPTT)	PT/INR/aPTT $\leq 1.5 \times \text{ULN}$

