### 5.1.2 Inclusion Criteria – Expansion Part A (GEN3014 Single Cohorts)

Each potential subject must fulfill all of the following criteria to be eligible for inclusion in the Expansion Part A of the trial:

1. Must be at least 18 years of age.
2. Must sign an ICF prior to any Screening procedures. Where required by local or country specific regulations, each subject must sign a separate ICF if he or she agrees to provide samples for genomic biomarker analysis (DNA and RNA).
3. ECOG PS score 0, 1, or 2 for MM and AML; ECOG PS 0 or 1 for DLBCL.
4. Must have fresh bone marrow samples collected at Screening. This requirement does not apply to R/R DLBCL subjects who are suspected to have bone marrow involvement.
5. Criterion modified per Amendment 2.

5.1 Criterion modified per Amendment 3\_US-1.

5.2 Criterion modified per Amendment 4.

5.3 Has acceptable laboratory test results during the Screening period, as follows:

Parameter		Result
a.	Creatinine clearance (CrCl) or serum creatinine	CrCl $\geq 50$ mL/min estimated by Cockcroft-Gault (see Section 10.5) or serum creatinine $\leq 1.5 \times$ upper limit of normal (ULN)
b.	Serum alanine aminotransferase (ALT)	$\leq 2.5 \times$ ULN
c.	Serum aspartate aminotransferase (AST)	$\leq 2.5 \times$ ULN
d.	Total bilirubin	$\leq 2 \times$ ULN Note: A subject with Gilbert's syndrome may be included if total bilirubin is <math>\leq 3 \times</math> ULN and direct bilirubin is <math>\leq 1.5 \times</math> ULN
e.	Hemoglobin	$\geq 8$ g/dL ( $\geq 80$ g/L or $\geq 5$ mmol/L) for RRMM and R/R DLBCL Note: Red blood cell transfusion may be administered during Screening to meet this requirement
f.	Absolute neutrophil count	$> 1.0 \times 10^9$ /L ( $> 1,000/\mu\text{L}$ ) for RRMM and R/R DLBCL Note: G-CSF may be administered during Screening to meet this requirement
g.	Platelet count	$> 50 \times 10^9$ /L ( $> 50,000/\mu\text{L}$ ) for RRMM and R/R DLBCL Note: Platelet transfusion may be administered during Screening to meet this requirement
h.	Coagulation Status: Prothrombin time (PT), International normalized ratio (INR), activated	PT/INR/aPTT $\leq 1.5 \times$ ULN

	partial thromboplastin time (aPTT)	
--	------------------------------------	--

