### 5.1.3 Inclusion Criteria – Expansion Part B (Randomized H2H)

Each potential subject must fulfill all of the following criteria to be eligible for inclusion in the Expansion Part B of the trial:

1. Must be at least 18 years of age.
2. Must sign an ICF prior to any Screening procedures. Where required by local or country specific regulations, each subject must sign a separate ICF if he or she agrees to provide samples for genomic biomarker analysis (DNA and RNA).
3. ECOG PS score 0, 1, or 2.
4. Must have fresh bone marrow samples collected at Screening.
5. Has acceptable laboratory test results during the Screening period, as follows:

Parameter		Result
a.	Creatinine clearance (CrCl) or serum creatinine	CrCl $\geq 20$ mL/min (Cockcroft-Gault formula [see Section 10.5] or EGFR [MDRD] or CKD-epi)
aCZ	Creatinine clearance	See Section 10.15.1 for requirements per local health authorities
b.	Serum alanine aminotransferase (ALT)	$\leq 2.5 \times \text{ULN}$
c.	Serum aspartate aminotransferase (AST)	$\leq 2.5 \times \text{ULN}$
d.	Total bilirubin	$\leq 2 \times \text{ULN}$ , except in subjects with congenital bilirubinemia, such as Gilbert syndrome (direct bilirubin $\leq 2.0 \times \text{ULN}$ )
e.	Hemoglobin	$\geq 7.5$ g/dL ( $\geq 4.65$ mmol/L)  Note: Red blood cell transfusions are not permitted within 7 days before the laboratory test for eligibility review; recombinant human erythropoietin use is permitted
f.	Absolute neutrophil count	$> 1.0 \times 10^9/\text{L}$ ( $> 1,000/\mu\text{L}$ )  Note: (Granulocyte colony stimulating factor [G-CSF] use is permitted)

g.	Platelet count	$>50 \times 10^9/L$ ( $>50,000/\mu L$ ) if bone marrow is $>50\%$ involved in myeloma. Otherwise $\geq 75 \times 10^9/L$  Note: Platelet transfusions are not permitted within 7 days before the laboratory test for eligibility review
h.	Coagulation Status: Prothrombin time (PT), International normalized ratio (INR), activated partial thromboplastin time (aPTT)	$PT/INR/aPTT \leq 1.5 \times ULN$

6. A woman of reproductive potential must agree to use adequate contraception during the trial and for 12 months after the last GEN3014 or daratumumab SC administration. Adequate contraception is defined as highly effective methods of contraception (refer to Section 10.4 Appendix 4: Contraceptive Guidance and Collection of Pregnancy Information). In countries where 2 highly effective methods of contraception are required, both methods will be required for inclusion.

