##### **6.6.3.1.1 GEN3014 IV or Daratumumab SC Dose Delays**

If any of the following criteria are met and the toxicity is more than expected for the underlying MM, GEN3014 infusion or daratumumab injection must be held to allow for recovery from toxicity as noted below. If attribution is unclear, then GEN3014 or daratumumab should be held until recovery from toxicity as noted below:

The criteria for a delay are:

- Grade 4 hematologic toxicity, except for grade 4 lymphopenia
- Grade 3 thrombocytopenia with bleeding
- Febrile neutropenia
- Neutropenia with infection, of any grade
- Grade 3 or higher non-hematologic toxicities with the following exceptions:
  - Grade 3 nausea that responds to antiemetic treatment within 7 days
  - Grade 3 vomiting that responds to antiemetic treatment within 7 days
  - Grade 3 diarrhea that responds to antidiarrheal treatment within 7 days

- Grade 3 fatigue that was present at baseline or lasts for <7 days after the last administration of trial drug
- Grade 3 asthenia that was present at baseline or lasts for <7 days after the last administration of trial drug

Administration of trial drug may be restarted upon recovery from toxicity to Grade 2 or baseline, with the exception that Grade 2 laryngeal edema or Grade 2 bronchospasm must be fully recovered.

If a dose delay occurs, then PK and pharmacodynamic assessments should be performed on or relative to the actual day of trial drug administration, not on the original scheduled administration day.

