## **10.2 Appendix 2: Clinical Laboratory Tests**

The tests detailed in [Table 10-1](#) will be performed. The laboratory reports must be filed with the source documents.

Protocol-specific requirements for inclusion or exclusion of subjects are detailed in [Section 5](#). Evaluation of subject eligibility must be evaluated based on central laboratory data.

Furthermore, local laboratory values may be obtained at the discretion of the investigator and used for other clinical treatment decisions. The tests to be performed at central and local laboratories are detailed in [Table 10-1](#). Details on the collections, shipment of samples and reporting of results by the central laboratory are provided to investigators in the laboratory manual.

Local laboratory values for biochemistry, hematology, and coagulation must be obtained within 3 days prior to the first dose of each subject and reviewed prior to the first dose to ensure that the subject is still eligible. For subsequent doses, these laboratory values must be obtained the day before or on the day of each trial drug administration and reviewed by the investigator prior to each trial drug administration, to ensure the subject can be dosed according to the dosing instructions defined in the protocol.

For AE reporting of laboratory test abnormalities refer to Section [10.3.3](#).

Investigators must document their review of each laboratory safety report.

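### Protocol 6.6.2 item c: three of the six printed haemoglobin hold and release figures are wrong (8 g/L twice, for 80 g/L; 8 g/mL once, for 8 g/dL)

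*Protocol*

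**What the plan says.** Protocol 6.6.2 covers dose modification in Dose Escalation and Expansion Part A. It lists three haematology results for which a dose may be withheld, introduced by "During the trial, the GEN3014 dose can be held for the following laboratory results". Item c is the haemoglobin rule: "If hemoglobin is $<8$ g/dL ( $<8$ g/L or $<5$ mmol/L), hold dose until hemoglobin is $\geq 8$ g/mL". The bracket that follows gives the release value again as 8 g/L or 5 mmol/L. Each clause therefore prints three figures, offered as the same threshold in different units.

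The same haemoglobin level is an entry criterion for the same parts of the trial. Protocol 5.1.1 (Dose Escalation) prints "\geq 8$ g/dL ( $\geq 80$ g/L or $\geq 5$ mmol/L) for RRMM", and Protocol 5.1.2 (Expansion Part A) prints "\geq 8$ g/dL ( $\geq 80$ g/L or $\geq 5$ mmol/L) for RRMM and R/R DLBCL".

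The rule is used at the point of dosing. For doses after the first, Protocol 10.2 says of haematology, biochemistry and coagulation results that "these laboratory values must be obtained the day before or on the day of each trial drug administration and reviewed by the investigator" before the drug is given.

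**The concern.** Item c contradicts itself. A haemoglobin of 8 g/dL cannot equal 8 g/L, and the release value switches to g/mL, a unit used for haemoglobin nowhere else in the eligibility or dosing sections.

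The protocol gives several units so that a site can work in whichever its laboratory reports. Taken unit by unit, the line fails as follows:

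- **A site reporting in g/L** has no correct figure in either clause. On that figure alone, a subject at 20 to 75 g/L (2 to 7.5 g/dL) would not be held, and any held subject would be released at 8 g/L or more.
- **A site reporting in g/dL** has the right hold figure but no release figure in g/dL. The g/mL figure printed in its place could never be reached.
- **A site reporting in mmol/L** has correct figures in both clauses.

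Release timing has a consequence of its own. Under 6.6.2, a delay of more than 4 weeks from the last dose because of toxicity leads to discontinuation of GEN3014 unless the sponsor and investigator agree to resume.

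The data at stake are descriptive. Table 3-1 lists "Tolerability: Dose interruptions, delay, and dose intensity" as a tolerability endpoint for Dose Escalation, and SAP 5.5.1 tabulates delays and their reasons.

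**Working it through.** **Inputs, all from the protocol**

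- 6.6.2 item c, hold: below 8 g/dL, 8 g/L, 5 mmol/L.
- 6.6.2 item c, release: at or above 8 g/mL, 8 g/L, 5 mmol/L.
- 5.1.1 and 5.1.2, haemoglobin entry criterion: 8 g/dL, 80 g/L, 5 mmol/L.
- 5.1.3 (Part B), haemoglobin entry criterion: "\geq 7.5$ g/dL ( $\geq 4.65$ mmol/L". This is used only to obtain the protocol's own conversion from g/dL to mmol/L.

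**Conversions**

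- 1 g/dL = 10 g/L = 0.01 g/mL.
- From the Part B pair, 4.65 / 7.5 = 0.62 mmol/L per g/dL.

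**Does the eligibility set agree with itself?**

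- 8 g/dL × 10 = 80 g/L, as printed.
- 8 × 0.62 = 4.96 mmol/L, which rounds to the printed 5.
- In reverse, 5 / 0.62 = 8.06 g/dL = 80.6 g/L.

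The entry criterion is consistent in all three units, so 80 g/L is the intended g/L figure.

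**Does item c agree with itself?**

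| Clause | Printed | In g/dL | In mmol/L | Ratio to 8 g/dL | Correct? |
|---|---|---|---|---|---|
| Hold | 8 g/dL | 8 | 4.96 | 1 | Yes |
| Hold | 8 g/L | 0.8 | 0.50 | 0.1 | No |
| Hold | 5 mmol/L | 8.06 | 5 | about 1 | Yes |
| Release | 8 g/mL | 800 | 496 | 100 | No |
| Release | 8 g/L | 0.8 | 0.50 | 0.1 | No |
| Release | 5 mmol/L | 8.06 | 5 | about 1 | Yes |

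One of three figures is wrong in the hold clause and two of three in the release clause, giving three of six. Replacing 8 g/L with 80 g/L in both places and 8 g/mL with 8 g/dL makes all six agree with one another and with 5.1.1 and 5.1.2.

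**The case against.** The arithmetic is not in dispute; the argument is over how much it matters.

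- **The g/dL trigger is correct and comes first.** A value of 75 g/L is 7.5 g/dL, so the leading condition still catches that subject if the reader converts. This stands, and it means the line contradicts itself visibly rather than silently giving a wrong instruction. It does not help with release, where no g/dL figure is printed.
- **The wrong values are implausible.** A clinician would probably recognise 0.8 g/dL and 800 g/dL as slips. This also stands, but an operative dosing rule should not depend on the reader spotting the error.
- **The rule is permissive and not the only safeguard.** The dose can be held rather than must be. The note after item c allows continuation to be discussed with the medical monitor when cytopenia is attributed to marrow disease, and permits transfusion. Any adverse event can justify postponing a dose by up to 4 weeks, and grade 4 anaemia is a DLT in Dose Escalation (AML has its own pancytopenia rule). All of this limits the harm.
- **The reach may be narrow.** Section 4.3.2 records that 16 mg/kg has already been chosen as the RP2D, and Part B has its own grade-based rule in 6.6.3.1.1: "GEN3014 infusion or daratumumab injection must be held to allow for recovery from toxicity as noted below". The documents do not say how many subjects remain on treatment under 6.6.2, so the number affected is unknown.
- **A letter may not be enough.** Section 10.1.4 requires a formal amendment for changes to the protocol, and the documents describe no clarification-letter route. This bears on any interim step, not on the need for the correction.

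These points argue against a higher severity. None of them makes the printed line right, and nothing elsewhere in the protocol corrects it.

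**Conclusion.** The concern holds: item c is wrong as written. Two figures are one tenth of the intended value and one is 100 times it. The intended values are certain from the protocol's own entry criteria, without any outside source.

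The effect is confined to dosing decisions in Dose Escalation and Expansion Part A, and to the descriptive delay and dose-intensity summaries that follow from them. Those summaries are a listed endpoint in Dose Escalation only. ORR, the Part B comparison, the sample sizes and the SAP methods do not use these figures. The point should be fixed because it is a decision threshold that investigators apply before each dose, not because large harm is likely.

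One assumption remains: that the text reflects the source document. A reading error would have had to drop a zero twice and change a unit within one line, while leaving 80 g/L intact in the eligibility tables. That is unlikely, but the source PDF was not available to confirm it.

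**What to change.** Replace item c with:

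> If hemoglobin is <8 g/dL (<80 g/L or <5 mmol/L), hold dose until hemoglobin is ≥8 g/dL (≥80 g/L or ≥5 mmol/L).

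Make the correction in the next protocol amendment. Until then, send a clarification letter to Dose Escalation and Part A sites, provided the sponsor is satisfied that this is compatible with Section 10.1.4. There is precedent for the amendment route: Amendment 5 corrected the direction of the calcium change in Table 10-2 and a saline flush volume in 10.15.1.

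The cost is one letter and one line of text. The clinical threshold, data collection, SAP and sample size are unchanged.
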